2.8 Risk/Benefit of the itouch Sure Pelvic Floor Exerciser

The itouch Sure Pelvic Floor Exerciser is manufactured by TensCare Ltd., [name].

In accordance with its regulatory obligation for FDA clearance and European CE approval, Tenscare Ltd. are required to have completed a risk/benefit analysis and Full Failure Modes Effects Analysis (FMEA), in line with ISO14971, for all stages of design, manufacturing, storage, shipping and clinical use of this device. As evidenced by their continued certification to ISO13485, TensCare Ltd also maintain updated records in line with Medical Device Directive 93/42/EC, as amended by 2007/47/EC, to ensure the continued device safety and performance profiles.

The risk/benefit for the itouch Sure Pelvic Floor Exerciser is well established since the device is cleared by the FDA through the 510 (k) premarket notification process (K103698) in the USA and also CE Mark approved in Europe.

The Manufacturer and User Facility Device Experience (MAUDE) database details medical device reports submitted to the FDA in the USA by mandatory reporters (manufacturers, importers and device user facilities) and voluntary reporters such as health care professionals, patients and consumers. To date, there are no recorded issues filed for the use of the itouch Sure Pelvic Floor Exerciser on the MAUDE database.

The use of the device in this study poses no additional risks to the subjects since it is being used in accordance with the Instructions for Use (IFU for this device as used in this study are believed to be compliant with the US FDA 501(k) label).

3 Objectives

3.1 Primary Objective

The primary objective of this clinical study is to evaluate and compare the safety and performance profile of the Neurotech Vital Compact device (delivering electrical stimulation through external electrodes) and the itouch Sure Pelvic Floor Exerciser (delivering electrical stimulation through an internal vaginal probe) for the treatment of stress urinary incontinence following a 12-week treatment program.

3.2 Secondary Objectives

The secondary objectives of this clinical study are to further evaluate the safety and performance of the Neurotech Vital Compact device compared to the itouch Sure Pelvic Floor Exerciser.

4 Study Design

This is a prospective, randomised, controlled, single-blind, multi-site clinical study to be conducted in the United States of America (USA) employing Neuromuscular Electrical Stimulation (NMES) to stimulate the pelvic floor muscles of women suffering from stress urinary incontinence.

Approximately one-hundred and eighty (180) female patients diagnosed with stress urinary incontinence will be enrolled in this study. All patients who are considered eligible to participate in the clinical study and give consent will be randomised to complete either a 12-week treatment programme with the Neurotech Vital Compact device or a 12-week treatment programme with the itouch Sure Pelvic Floor Exerciser. The 12-week treatment programme will be completed by the subjects at home with treatment with the device in accordance with the device Instructions for Use.

Subjects included in the clinical study will be evaluated at screening, on enrolment into the study (baseline) and during the 12-week treatment programme at 4 and 12 weeks. A telephone call will be made at 1 week to check on the patient's progress. In addition, subjects will be evaluated at 26 week following their commencement of the treatment.

Telephone support will be available throughout the duration of the study. A clinical study Schedule of Events is presented in Appendix I.

All information provided to the subjects will be provided in a language in which they are conversant for both reading and speaking which will include: Incontinence Quality of Life Questionnaire (I-QOL) (Appendix V); Instructions for Use for the allocated device (Appendices XI and XII); Medical, Epidemiologic and Social Aspects of Aging Urinary Incontinence Questionnaire (MESA) (Appendix VII) ; Pelvic Organ Prolapse/Urinary Incontinence Sexual Questionnaire (PISQ-IR) (Appendix VI); Patient Global Impression of Improvement (PGI-I) (Appendix IX); the voiding diary (Appendix VIII); patient information sheet and consent documents (Appendix X).

5 Trial Endpoints

5.1 Primary Endpoint

The primary endpoint is defined as the proportion of subjects considered to have achieved ‘significant improvement’ following a provocative pad weight test at 12 weeks compared to baseline.

‘Significant improvement’ is defined as a greater than 50% reduction in pad weight from baseline.

5.2 Key Secondary Endpoints to Support Indication for Use

The following key secondary endpoints will each be analysed, for superiority, at a 5% two-sided significance level with a view to support labelling. In order to control the type I error rate the endpoints will be analysed in the following hierarchy (see Section 14.0 Statistical Plan for further details). If any endpoint in the sequence fails to show a statistically significant difference then the inference is that there is insufficient evidence both for that endpoint and the subsequent endpoints in the hierarchy.

- Between group comparison of mean change, with respect to baseline, in urine leakage in a provocative pad weight test at Week 12;
- Within Neurotech Vital Compact group estimate of mean change, with respect to baseline, in urine leakage in a provocative pad weight test at Week 12;
- Between group comparison of mean change, with respect to baseline, in urine leakage in the 24-hour pad weight test at Week 12;
- Within Neurotech Vital Compact group estimate of mean change, with respect to baseline, in urine leakage in the 24-hour pad weight test at Week 12;
- Between group comparison of mean change, with respect to baseline, in the number of incontinence episodes/day recorded using a 7-day voiding diary at Week 12;
- Within Neurotech Vital Compact group estimate of mean change, with respect to baseline, in the number of incontinence episodes/day recorded using a 7-day voiding diary at Week 12;
- Between group comparison of the mean improvement, with respect to baseline, in Incontinence Quality of Life Questionnaire (I-QOL) score at Week 12;
- Within Neurotech Vital Compact group estimate of mean improvement, with respect to baseline, in Incontinence Quality of Life Questionnaire (I-QOL) score at Week 12;
- Between group comparison of mean change, with respect to baseline, in the number of pads used/day recorded using a 7-day voiding diary at Week 12;
- Within Neurotech Vital Compact group estimate of mean change, with respect to baseline, in the number of pads used/day recorded using a 7-day voiding diary at Week 12;
- Between group comparison of the proportion of subjects achieving dryness at Week 12 (<1g on the provocative pad weight test).

5.3 Secondary Endpoints - Other

Other secondary endpoints that will be evaluated at 4 weeks and 26 weeks are as follows:

- Proportion of subjects considered to have achieved significant improvement, defined as a greater than 50% reduction in pad weight, from baseline on the provocative pad weight test.
- Urine leakage on the provocative pad weight test (following standardized bladder-filling protocol).
- Urine leakage experienced by the subject at home in the 24-hour pad weight test;
- Incontinence episodes/day recorded using a 7-day voiding diary;
- Proportion of subjects achieving dryness (<1g on the provocative pad weight test)
- Improvement in quality of life assessed using the Incontinence Quality of Life Questionnaire (I-QOL);
- Number of pads/day recorded using a 7-day voiding diary;
- Dryness, defined as a pad weight of less than 1.3g on the 24-hour pad weight test (including an evaluation at 12 weeks);
- Proportion of subjects considered to have achieved significant improvement, defined as a greater than 50% reduction in pad weight, from baseline on the 24-hour pad weight test (including an evaluation at 12 weeks).

Other data that will be evaluated are as follows:

- Proportion of subjects achieving dryness at Week 12 in each group (<1g on the provocative pad weight test).
- Within Neurotech Vital Compact group estimate of mean change, with respect to baseline, in sexual function as measured by the Pelvic Organ Prolapse/Urinary Incontinence Sexual Questionnaire (PISQ-IR) (Appendix VI) at Week 12;
- Between group comparison of mean change, with respect to baseline, in sexual function as measured by the Pelvic Organ Prolapse/Urinary Incontinence Sexual Questionnaire (PISQ-IR) at Week 12;
- Within Neurotech Vital Compact group estimate of patient response to the Patient Global Impression of Improvement (PGI-I) at Week 12.
- Between group comparison of patient response to the Patient Global Impression of Improvement (PGI-I) at Week 12;
- Safety in relation to adverse events and device deficiencies reported;
- Evaluation of reduction in urine leakage on the provocative pad weight test in relation to the mean intensity of the stimulation delivered during the 12-week treatment programme;
- Evaluation of the reduction in urine leakage on the provocative pad weight test at Week 12 in relation to the BMI category (underweight/normal/overweight/obese) of the subjects;
- Evaluation of the reduction in urine leakage on the provocative pad weight test at Week 12 in relation to the baseline severity of stress urinary incontinence of the subjects;
- Device compliance of the Neurotech Vital Compact device with the treatment protocol during the 12-week treatment programme;
- Device compliance of the itouch Sure Pelvic Floor Exerciser with the treatment protocol during the 12-week treatment programme.

6 Trial Population

6.1 Number of Subjects

Subjects who meet all of the inclusion and none of the exclusion criteria will be randomized into the study until approximately 180 healthy female subjects have completed the study.

6.2 Inclusion Criteria

1. Subjects who are female and at least 18 years of age, and not more than 65 years of age.
2. Subjects who have signed the informed consent form prior to any study related activity.
3. Subjects who have previously tried and failed to improve their condition using Kegel exercises.
4. Subjects who have been clinically diagnosed with stress urinary incontinence and demonstrate a greater than or equal to 3g urine leakage and a less than or equal to 90g urine leakage ($\geq 3g$ and $\leq 90g$) following a bladder-filling protocol and then a standardised stress test (provocative pad weight test) at the baseline assessment.
5. Subjects who score 9 or less (≤ 9) out of 18 for the Urge Incontinence Questions and are confirmed as having predominant stress urinary incontinence on the Medical, Epidemiologic and Social Aspects of Aging Urinary Incontinence (MESA) Questionnaire completed at the screening assessment.
6. Subjects with a Body Mass Index of $\leq 35 \text{ kg/m}^2$.
7. Subjects of child-bearing potential who are using a highly effective contraceptive method (established use of oral, injected, implanted hormonal method of contraception or barrier method of contraception with spermicide).
8. Subjects who are willing not to seek any other treatment for stress incontinence during the study period.
9. Subjects who are able to give voluntary, written informed consent to participate in this study and from whom consent has been obtained.
10. Subjects who are able to understand this study and are willing to complete all the study assessments.

6.3 Exclusion Criteria

1. Subjects who have an existing medical condition that would compromise their participation in the study, e.g. reduced sensory perception in the contact area of the stimulation electrodes; scars or vaginal tissue wounds, lesions or inflamed/infected areas in the contact area of the stimulation electrodes; vaginal bleeding between menstrual periods; uncontrolled diabetes.
2. Subjects who have a physical condition that would make them unable to perform the study procedures, e.g. pelvic or hip surgery within the past 6 weeks.
3. Subjects who have been diagnosed with Chronic Obstructive Pulmonary Disease (COPD).
4. Subjects with a history of an underlying neurological condition, e.g. Multiple Sclerosis, Parkinson's disease, epilepsy.
5. Subjects with any bladder abnormality that would affect the urinary flow through the lower urinary tract including signs or symptoms of an active urinary tract infection, abnormal bladder capacity (e.g., $>300 \text{ cc}$), post void residual volume $>200 \text{ cc}$, spastic bladder, vesico-ureteral reflux or bladder stones.
6. Subjects with a blood clotting disorder or who are taking anti-coagulant medications.

7. Subjects who have previously had any uro-gynaecological related surgery that would affect the pelvic floor muscles or urinary flow through the urethra (excluding hysterectomy).
8. Subjects who have previously had pelvic floor radiation.
9. Subjects who have previously been treated for stress incontinence with injectable bulking agents and/or vaginal probes within the past 6 months.
10. Subjects with a clinical diagnosis of prolapse greater than Stage 2.
11. Subjects who are pregnant or could be pregnant.
12. Subjects who are less than 6 months post-partum or who are lactating.
13. Subjects who have any conductive intra-uterine devices or metal implants in the pelvic area, including hip and lumbar spine.
14. Subjects with pelvic pain or fibromyalgia or paravaginal defect.
15. Subjects with an active implanted medical device (i.e. pacemaker, insulin pump etc.) or conditions that may be adversely affected by electrical stimulation (e.g. cardiac arrhythmias).
16. Subjects with a current or active history of pelvic cancer and/or subjects with a life expectancy of less than 12 months.
17. Subjects who are currently involved in any injury litigation claims.
18. Subjects who have participated in a clinical study in the last 3 months or any previous clinical study with Bio-Medical Research Ltd.
19. Subjects who have been committed to an institution by virtue of an order issued either by the courts or by an authority.

6.4 Withdrawal Criteria

During the course of this study, subjects may be withdrawn, or may elect to withdraw through any of the listed following reasons below. However all subjects will be assessed on an individual basis when clarifying their withdrawal and for this reason, measurable parameters cannot be specifically defined for the withdrawal criteria below:

- Subject's rescission of consent.
- Any adverse event, related to the device or not, which may endanger the well-being of the subject if they were not withdrawn.
- Subject non-compliance or protocol violation.
- Subject unable to meet the protocol requirements.
- Development of a medical condition or illness which may compromise safety of the subjects or invalidate the results of the study.

The Investigator will clearly document the date and reason(s) for withdrawal in the Case Report Form.

All subjects discontinued from the study due to an adverse event will be followed up by the Investigator until resolution or condition has stabilised.

Subjects who are withdrawn prior to the completion of the baseline assessments only will be replaced.

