6.5 Monitoring for Subject Compliance

Subject compliance will be based on three assessments, namely, the level of completion of patient 7-day voiding diary, attendance at scheduled follow-up visits plus evaluation of the internal memory of the Neurotech Vital Compact device and the itouch Sure Pelvic Floor Exerciser or the Device Record (diary) to check daily use parameters and schedules.

7 Study Treatments

One device will be issued to each randomized subject in a single-blinded manner. The investigator and those administering the 1-hour provocative stress test, evaluating adverse events and reviewing diary data are to remain blinded regarding treatment assignment.

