8.11.1 Early Termination

If a subject starts treatment discontinues before completing all study visits, she is to be asked to return to the clinic to complete a Visit 4 visit as an early termination visit (if prior to that visit) or a Visit 5 visit (if after Visit 4 has taken place).

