1.6.2 GENERAL PRINCIPLES

Data will be summarized using descriptive statistics. For continuous measures, this will include number (N), mean, standard deviation, median, and range (minimum and maximum). For categorical measures, counts and percentages will be provided. Data will be summarized separately for each randomized arm under the principles of intent to treat, unless otherwise noted. All statistical tests will be conducted at $\alpha = 0.05$, two-sided significance level, unless otherwise stated. The day of randomization is considered as Day 1 and the day prior to randomization is Day -1. Summaries will be based on the database visits, regardless of the relative day of the visit; early termination visits are to be collected as Week 12 and all follow-up assessments are collected as Week 26.

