2 ANALYSIS

2.1 ANALYSIS POPULATIONS

The primary analysis population will be the intent to treat (ITT) population. This will include all randomized subjects. Subjects will be summarized according to their randomized assignment. If there are randomized subjects who do not use the device at least once, a modified ITT (mITT) population will be defined to exclude such subjects and this population will be used in place of ITT.

A per-protocol (PP) population will also be evaluated for the primary endpoint. This population will consist of subjects who:

- Signed informed consent
- Met inclusion/exclusion criteria
- Were treated per randomized assignment
- Had 12 week outcome data available
- Met study compliance criteria
- No significant protocol deviations

Prior to locking the database, the PP criteria will be reviewed, additional criteria will be added if needed, and a listing of PP violations will be generated. The Sponsor/CRO will review this list and determine exclusions from this population. The final list of PP criteria and exclusions will be documented prior to unblinding.

The Safety population will include all randomized subjects who used the device at least once. Subjects will be summarized according to the actual device used, rather than the randomized assignment.

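### Protocol 6.4 allows withdrawal for non-compliance without separating device use from outcome follow-up, so early or imputed values replace some true Week 12 outcomes in the ITT analysis

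*Protocol*

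**What the plan says.** Protocol 6.4 opens: "During the course of this study, subjects may be withdrawn, or may elect to withdraw through any of the listed following reasons below". The listed reasons include "Subject non-compliance or protocol violation" and, separately, inability to meet the protocol's requirements. The section adds that "measurable parameters cannot be specifically defined for the withdrawal criteria below". Replacement is limited: "Subjects who are withdrawn prior to the completion of the baseline assessments only will be replaced". Nothing in 6.4 distinguishes a woman who stops the device from one who leaves the study.

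Protocol 6.5 gives compliance a wide meaning: "Subject compliance will be based on three assessments, namely, the level of completion of patient 7-day voiding diary, attendance at scheduled follow-up visits", together with the device memory or device record. It gives no cut-off.

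Protocol 8.11.1 is the only provision for outcomes after discontinuation. If Visit 4 has not yet taken place, "she is to be asked to return to the clinic to complete a Visit 4 visit as an early termination visit". SAP 1.6.2 bases summaries on the database visit rather than the study day, and "early termination visits are to be collected as Week 12".

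On the analysis set, SAP 2.1 states: "The primary analysis population will be the intent to treat (ITT) population. This will include all randomized subjects". Compliance and significant deviations are criteria for the per-protocol set only.

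**The concern.** An ITT comparison at Week 12 needs the Week 12 outcome of every randomised woman, including those who used the device poorly or broke a protocol rule. Section 6.4 lets the study end scheduled follow-up for exactly those women, by case-by-case judgement. The analysis plan has no need of this, because SAP 2.1 already removes non-compliers and deviators where that belongs, in the per-protocol set.

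At stake is the validity of a non-inferiority claim with a 5-point margin. If the values that stand in for the true Week 12 outcomes are off by different amounts in the two arms, the device difference moves. Three features make an imbalance possible:

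- Women know which device they have.
- The prescribed load differs: 84 vaginal-probe sessions against 60 external sessions (SAP 3.7.3).
- Device compliance is monitored by unblinded staff (Protocol synopsis, Single-Blind Status; 2.5).

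**Working it through.** **1. What happens to a woman withdrawn before Week 12**

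| | Attends early-termination visit | Does not attend |
|---|---|---|
| ITT membership | Kept | Kept |
| Value used as Week 12 | Pad test on the day she attends, for example Week 5 (8.11.1, SAP 1.6.2) | Multiple imputation from baseline and Week 4 leakage (SAP 2.3.2.1) |
| LOCF sensitivity analysis | Unchanged, because a value exists | Last earlier value carried forward |
| Tipping-point analysis | Not varied, because it works only on missing values (SAP 2.3.2.2) | Varied over all combinations |
| Scheduled Week 12 and Week 26 visits | No provision | No provision |

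The modified ITT rule in SAP 2.1 does not alter this. It drops only women who never used the device, and the first session is completed in clinic at baseline (8.10.1).

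In the first column no planned analysis tests the substitution. Protocol 2.3 expects training effects to accumulate over the 12 weeks, so an early reading need not equal the Week 12 value. In the second column the imputation model holds only baseline, Week 4 and Week 12 leakage. It has no term for arm, compliance or reason for withdrawal, so a non-complier is credited with the outcome of women in either arm who had similar earlier leakage.

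**2. The plan's own figure**

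Inputs from Protocol 10.2: 52% and 71%, margin 5 points, one-sided 0.025, 90% power. With average proportion (0.52 + 0.71)/2 = 0.615:

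n = (1.960 + 1.282)² × 2 × 0.615 × 0.385 / (0.71 − 0.52 + 0.05)² = 86.4, so 87 per group.

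The planned 87 is reproduced, and this point does not dispute it.

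**3. Size of the possible bias**

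Let w be the proportion withdrawn in an arm, and g the response credited to withdrawn women minus their true Week 12 response. Then

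bias in the difference = w(test) × g(test) − w(control) × g(control).

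The documents give neither w nor g, so the following are assumed.

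- Same gap in both arms, withdrawal differing by 5 to 10 points, gap 20 to 40 points: 0.05 × 0.20 = 1.0 point, up to 0.10 × 0.40 = 4.0 points.
- Withdrawal 15% (test) and 5% (control), credited response 52% in both arms, true response 20% to 30%: 0.10 × 0.32 = 3.2 points, down to 0.10 × 0.22 = 2.2 points, favouring the test device. Swapping the withdrawal rates reverses the sign.
- Equal withdrawal of 10%, credited 71% and 52%, true 20%: 0.10 × 0.51 − 0.10 × 0.32 = 1.9 points. Equal withdrawal cancels the bias only when the gaps are equal too. This case assumes arm-specific imputation, which the SAP code does not use, so it shows the principle only.

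**4. What 1 to 4 points would do at the margin**

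Suppose the true rates sit on the null boundary, 47% against 52%, with 90 per arm. The standard error is √[(0.47 × 0.53 + 0.52 × 0.48)/90] = 7.4 points. A bias towards the test device of 1 point gives P(Z > 1.96 − 1/7.44) = 3.4%. A bias of 4 points gives P(Z > 1.96 − 4/7.44) = 7.7%. The nominal level is 2.5%.

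**5. Precision**

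The step from 87 to 90 covers 1 − 87/90 = 3.3% loss. If 10% gave no information, 81 per group would leave 89.3% power (unpooled variance). Bias is the larger concern.

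**The case against.** The strongest reply is that the plan already deals with these women. They remain in the ITT set as randomised. Those who attend the early-termination visit have a pad test result. The rest are imputed, and the tipping-point analysis runs every responder and non-responder combination for them. This stands to a large extent: a reader might infer that these outcomes are simply lost, or that the ITT set shrinks to the per-protocol set, and the documents do not support either. What remains is that an early value is treated as an observed Week 12 value and escapes every sensitivity analysis.

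A reader might also infer that unblinded staff decide who is withdrawn. No section says so. Section 6.4 names only the investigator, who documents the reason. The opening of Protocol section 7 keeps the investigator and those reviewing diary data blinded, and 11.5 separates the trainer from the assessor. Unblinded knowledge of device use could influence a decision, but that is a possibility and not a stated procedure. Poor diary keeping in particular is reviewed by blinded staff.

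Finally, 6.4 is permissive. Women may be withdrawn after individual assessment, and 12.5 speaks of corrective and preventative action for repeated and serious compliance failures. The clause may be used rarely. That limits the likely size but does not explain why such women should leave outcome follow-up at all.

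**Conclusion.** The point holds in this form: 6.4, 8.11.1 and SAP 1.6.2 together allow the primary ITT comparison to use early or imputed values in place of true Week 12 outcomes for women withdrawn over conduct, with no criteria for who they are.

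The 1 to 4 points should not be read as an estimate. They rest wholly on assumed withdrawal rates and response gaps, they take the gap as equal in both arms, and they do not model early-termination readings separately. The direction is unknown. If the planned 19-point advantage is real, even 4 points against the test device would leave an expected lower limit of about 19 − 4 − 1.96 × 7.1 = 1.1 points, well above −5. The weakness matters most if the devices perform similarly, which is where a non-inferiority margin has to do its work. It is a moderate weakness that is cheap to remove.

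**What to change.** - **Protocol 6.4:** state that, after randomisation, non-compliance, protocol violation or inability to meet protocol requirements is not by itself a reason to end outcome follow-up. These women attend Visit 4 at Week 12 (± 7 days) and Visit 5 at Week 26 (± 14 days) unless they withdraw consent.
- **Protocol 8.11.1 and SAP 1.6.2:** an early-termination assessment does not replace the scheduled Week 12 visit, and a value from outside the Week 12 window is not analysed as an observed Week 12 outcome. If no in-window value exists, the outcome counts as missing and so enters the imputation and the tipping-point analysis.
- **Protocol 8.10.1:** reconcile its withdrawal of women who cannot show competent device use with the sections above.
- **SAP 2.1:** handle non-compliance only through the per-protocol exclusions.

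None of this takes a position on when device use should stop.

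The cost is a short protocol and SAP amendment and some extra effort to bring these women back. Both visits are already in the schedule of events; the documents give no budget, so the effort cannot be priced. Observed response rates may be slightly lower because non-compliers are measured.
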